8 ADDITIONAL ANALYSES

8.1 Vital Signs

Vital sign measurements at screening (if not performed on the same day as screening, VS is to be performed prior to study vaccination) including respiratory rate, blood pressure, pulse rate, and temperature (oral or via forehead/ear reader) will be summarized as continuous variables.

Descriptive statistics for vital sign results at screening will be presented by the study vaccine group for all participants in the Safety Analysis Set, including means and SDs, median, minimum, and maximum. A by-participant listing of vital signs will be provided.

8.2 Physical Examinations

Physical examination at screening (if not performed on the same day as screening, PE is to be performed prior to study vaccination) includes height and weight, cervical and axillary lymph nodes, heart, and any other symptom-directed examination.

Symptom-directed (targeted) physical examination performed at screening and unscheduled visits will be summarized by study vaccine group and by body system. For each body system examined, the number and percentage of participants with normal/abnormal results will be reported. The calculation of abnormal results will also be broken out by whether the abnormal result was considered clinically significant or not.

9 CONDUCT OF ANALYSES

The first interim analysis (or called 1st Day 29 primary analysis) will be conducted when all available immunogenicity data (IgG, Nab, and hACE2) and safety data for **the group receiving ancestral strain NVX-CoV2373** through Day 29 have been entered, reviewed, and all queries related to the data have been addressed.

The secondary interim analysis (or called 2nd Day 29 primary analysis) will be performed when all available immunogenicity data (IgG, Nab, and hACE2) and safety data for **the group receiving updated Novavax COVID-19 Vaccine based on recent variant(s)** through Day 29 have been entered, reviewed, and all queries related to the data have been addressed.

The two interim analysis (both Day 29 primary analysis) may be combined depending on the processing of enrollment of participants in the group receiving **ancestral strain NVX-CoV2373** and participants in the group receiving **updated Novavax COVID-19 Vaccine based on recent variant(s)**.

Final analysis will be conducted when all available safety data throughout the study (from Day 1 through EoS) have been entered, reviewed, and all queries related to the data have been addressed.

10 COMPUTER METHODS

Statistical analyses will be performed using SAS® version 9.4 or higher in a Windows environment.

11 DATA HANDLING CONVENTIONS

All output will be incorporated into Microsoft Word or Excel files, or Adobe Acrobat PDF files, sorted and labeled according to the International Conference on Harmonisation (ICH) recommendations, and formatted to the appropriate page size(s).

Tabulations will be produced for appropriate demographic, baseline, and safety parameters. For categorical variables, summary tabulations of the number and percentage of participants within each category (with a category for missing data) of the parameter will be presented. For continuous variables, the number of participants, mean and standard deviation (SD), median, minimum, and maximum values will be presented.

All references to analysis of GMT/GMEU will be interpreted as analysis of the \log_{10} of titer values or ELISA Units.

The individual immunogenicity (Nab) titer values, IgG ELISA Units and hACE2 receptor-binding inhibition titer values recorded as below the LLOQ of the assay will be set to half LLOQ for the purposes of GMT/GMEU analyses. The LLOQ values will be provided by corresponding labs.

Medical history and AEs will be coded using MedDRA Version 25.0.

Each parameter will be reported with the below defined decimal numbers in [Table 5](#).

Table 5: Decimal Numbers for Parameters

Parameter	Number of Decimal
Number of participants (eg, N, N1, N2, n)	0
Percentage (%)	1
Mean	1 more decimal than raw data
Standard Deviation (SD)	1 more decimal than mean
Median, Min, Max	as same decimal as raw data
GMT, GMFR _{Post/Pre} , GMR _{312/307} , their corresponding 95% CIs	1
GMEU, GMFR _{Post/Pre} , GMR _{312/307} , their corresponding 95% CIs	1
SCR (%), their corresponding 95% CIs	1

11.1 Baseline Definitions

For all analyses, baseline is defined as the last non-missing measurement prior to the first administration of the study material. For immunogenicity analysis, baseline will be the result from the sample drawn on the day of vaccination (Day 1).

11.2 Adjustments for Covariates

Not applicable.

11.3 Multiple Comparisons/Multiplicity

Not applicable.

11.4 Withdrawals, Dropouts, and Loss to Follow-up

Participants are free to withdraw from the study at any time upon written request. Participant participation in the study may be stopped at any time at the discretion of the investigator or at the request of the sponsor.

Participants may refuse further procedures (including study vaccination) but are encouraged to remain in the study for safety follow-up. In such cases where only safety is being conducted, participant contact could be managed via telemedicine contact (eg, telephone, web chat, video, FaceTime).

Participants who withdraw, are withdrawn or terminated from this study, or are lost to follow up after signing the informed consent form (ICF) but prior to first study vaccination may be replaced. Participants who receive study vaccine and subsequently withdraw, discontinue, are terminated from the study, or are lost to follow-up will not be replaced.

Whenever possible, any participant who withdraws from the study prematurely will undergo all EOS assessments. Any participant who fails to return for final assessments will be contacted by the site in an attempt to have them comply with the protocol.

11.5 Missing, Unused, and Spurious Data

The status of participants who fail to complete final assessments will be documented in the electronic case report form (eCRF). Data that would have been collected at subsequent visits will be considered missing.

When tabulating AE and Concomitant Medications (exclusive of vaccinations prior to Dose 1) data, partial dates of event onset will be handled as follows:

- If the day of the month is missing, the onset date will be assumed to be the date of the Day 1 vaccination or first of the month, whichever is later, in order to conservatively report the event as treatment-emergent.
- If the onset day and month are both missing, the event onset will be coded to the date of the Day 1 vaccination or 1st January of the year, whichever is later, in order to conservatively report the event as treatment-emergent.

- A completely missing onset date will be coded as the date of the Day 1 vaccination, unless the end date suggests it could have started prior to this in which case impute the 1st January of the same year as the end date.
- No imputations will be made to event ending dates.
- When imputing a start date ensure that the new imputed date is prior to the end date of the AE or medication.

When tabulating Medical History or Previous Vaccination data, partial start dates of event will be handled as follows:

- For start date with a missing day and/or month, impute a missing day as the first of the month, and a missing month as January. The resulting date should be prior to the Day 1 vaccination and before the end date (full or partial date). A partial start date with an entirely missing ending date should result in a query to the site.
- For start date with a missing year, impute the year to be year of the ending date if it exists. Otherwise, the missing start date will be kept as missing.

For tabulations of AE, a top-level summary will be generated to report treatment-related AEs according to two conventions:

- No imputation of missing relationship to test article
- Consider the event to be treatment-related to test article.

Similarly, the top-level summary will report severe AEs according to two conventions:

- No imputation of missing severity
- Consider the event to be severe

Detailed presentation of AE data by SOC and preferred terms will be generated without first imputing missing relationship nor severity. As with missing dates, queries to the site should be undertaken before employing the reporting conventions described above.

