### 8.1.3 Timeframe for Collection

All AEs captured following the procedures listed in the SOE ([Table 1](#)) will be recorded on the AE page of the eCRF.

Medical occurrences that begin prior to administration of the study vaccine will be recorded on the Medical History/Current Medical Conditions section of the eCRF, not the AE section.

All unsolicited AEs of any severity will be collected from the time of study vaccination through 28 days after study vaccination. After Day 29, unsolicited AEs classified as MAAEs attributed to study vaccine will be collected until EOS.

All AESIs/PIMMCs will be collected from the time of study vaccination through EOS.

All SAEs will be collected from signing of informed consent until completion of the EOS.

All vaccine administration errors, MAAEs, SAEs, cases of multisystem inflammatory syndrome, and hospitalized or fatal cases of COVID-19 following vaccination must be reported based on local regulatory reporting guidance for safety events.

At any time after completion of the EOS visit, if an Investigator learns of an SAE that could reasonably be considered related to study vaccine, he/she should promptly notify the Sponsor.

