6.2 Prior and Concomitant Medication and Vaccination

Prior and concomitant medications include recent (\leq 90 days) and current medications, including non-COVID-19 vaccinations. All COVID-19 vaccines administered prior to screening will be recorded in the vaccine history eCRF. After Day 29, all COVID-19 vaccines, and only concomitant medications and other vaccines that have caused or are used to treat an AE will be recorded.

The number (percentage) of participants who record one or more prior/concomitant medications (including vaccines) recorded in the prior/concomitant medications eCRF will be summarized by the study vaccine group and preferred drug name as coded using the WHO drug dictionary for all participants in the Safety Analysis Set. Multiple occurrences of medication usage for a participant will be counted only once within an anatomical therapeutic chemical (ATC) term and standardized medication name.

A by-participant listing of treatment-emergent new concomitant medications (including vaccines) will be presented.

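### The SAP's partial-date rule moves an onset known to precede vaccination to Day 1, mainly affecting the listing of new concomitant medications

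*SAP*

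**What the plan says.** SAP section 11.5 introduces the rules with "When tabulating AE and Concomitant Medications (exclusive of vaccinations prior to Dose 1) data, partial dates of event onset will be handled as follows". Two of them concern this point:

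- Day missing: "the onset date will be assumed to be the date of the Day 1 vaccination or first of the month, whichever is later".
- Day and month missing: "the event onset will be coded to the date of the Day 1 vaccination or 1st January of the year, whichever is later".

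Both give the same reason, which is to err towards counting the event as treatment-emergent. Three further provisions in the section bear on how far the rules reach:

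- A wholly missing onset goes to Day 1 "unless the end date suggests it could have started prior to this in which case impute the 1st January of the same year", meaning the year in which the record ends.
- When a start is imputed, the programmer must "ensure that the new imputed date is prior to the end date of the AE or medication".
- The section closes by saying that, as with missing dates, "queries to the site should be undertaken before employing the reporting conventions described above".

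The output most exposed is in SAP section 6.2: "A by-participant listing of treatment-emergent new concomitant medications (including vaccines) will be presented".

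For adverse events, Protocol section 8.1.3 narrows the field: "Medical occurrences that begin prior to administration of the study vaccine will be recorded on the Medical History/Current Medical Conditions section" of the case report form rather than the adverse event section. The same section collects serious adverse events from signed consent onwards.

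**The concern.** Defaulting to Day 1 is sensible when the onset could lie on either side of vaccination, that is, when the known month or year is the one in which the participant was vaccinated. Taking the later of two dates goes further. If the known month or year ended before Day 1, there is nothing left to resolve, yet the rule still returns Day 1 and the derived date contradicts the recorded one.

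Two outputs could carry the error. A drug taken for years could be listed as newly started on vaccination day. A serious event that began between consent and vaccination could be counted as treatment-emergent, because Protocol section 8.1.4.1 defines that status by occurrence or worsening on or after the dose.

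**Working it through.** No sample size, power or event count is involved, and the plan gives no figure to reproduce. The check is to apply the rule literally and see what it returns.

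**Rule as written.** Imputed start = max(Day 1, first of the known month), or max(Day 1, 1 January of the known year). If the known part lies before Day 1, the maximum is Day 1 by construction.

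**Test records.** Day 1 is set to 15 March 2023, which is an assumption for illustration. The last column applies the change proposed below.

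| Record | Known to start before Day 1? | SAP rule gives | Stopped by end-date check? | With the fix |
|---|---|---|---|---|
| Drug, 2015 only, ongoing | yes | 15 Mar 2023 | no | 1 Jan 2015 |
| Drug, Dec 2022, ongoing | yes | 15 Mar 2023 | no | 1 Dec 2022 |
| Serious event, Feb 2023, ongoing | yes | 15 Mar 2023 | no | 1 Feb 2023 |
| Serious event, Feb 2023, ended 20 Mar 2023 | yes | 15 Mar 2023 | no | 1 Feb 2023 |
| Drug, Feb 2023, ended 1 Mar 2023 | yes | 15 Mar 2023 | yes, but no replacement date given | 1 Feb 2023 |
| Event, Mar 2023, ongoing | no | 15 Mar 2023 | no | 15 Mar 2023 |
| Event, 2023 only, ongoing | no | 15 Mar 2023 | no | 15 Mar 2023 |
| Event, Apr 2023, ongoing | no | 1 Apr 2023 | no | 1 Apr 2023 |

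The first four rows are misdated. The fifth is blocked, but the SAP does not say what date to use instead. The last three are handled as intended and stay as they are.

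**How often the month alone settles the order.** Take every Day 1 in 2023 with equal weight (an assumption) and every true onset 1 to 30 days earlier, the longest screening window in Protocol section 6.1.1. That gives 365 × 30 = 10,950 pairs. In 5,577 of them the onset falls in an earlier calendar month: 5,577 / 10,950 = 50.9%. For onsets 1 to 90 days earlier, the look-back for recent medications in Protocol section 7.3, the figure is 27,477 / (365 × 90) = 27,477 / 32,850 = 83.6%. In all of these pairs, if the day is missing, taking the later date gives Day 1. These percentages describe the calendar. They are not estimates of how many trial records have a missing day.

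**Size of one misclassified serious event.** With 100 to 150 participants per group, 1/150 = 0.7% and 1/100 = 1.0%.

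**Comparison with the neighbouring rules.** A wholly missing onset can be placed before Day 1 if the end date points that way, whereas an ongoing record with a known pre-vaccination month cannot. The medical history rule in the same section keeps the known month or year and expects a result before Day 1. The SAP therefore already contains the logic that the two bullets lack.

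**The case against.** The strongest reply is that the rule reaches very little and errs in the safe direction. Most of that is right, and it rules out several broader readings.

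- *Every record with an earlier known month or year is misdated.* A reader might infer this from the two bullets alone. Site queries come first, and the end-date check keeps any record that ended on or before Day 1 from being set to Day 1. What remains is unresolved partial dates on records that are ongoing or end after Day 1.
- *The medication tables are distorted.* The table in SAP section 6.2 pools prior and concomitant drugs by preferred name, with no split at Day 1, so its counts do not move. Only the listing depends on the start date.
- *Treatment-emergent event rates are materially inflated.* Pre-vaccination occurrences belong in medical history, which has its own date rule. What is left is mainly a serious event between consent and Day 1. Protocol section 6.1.1 expects Screening and Day 1 to be combined where possible. The participant must still be judged medically stable and be vaccinated. Serious events are reported within 24 hours of awareness and followed up, so a permanently unknown day is unlikely.
- *The main result is at risk.* Titres, per-protocol membership and the non-inferiority tests do not use this rule, and all safety analyses are descriptive.

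The reply does not remove the defect. Queries reduce the number of partial dates, but the imputation rule exists for those that remain. The end-date check does nothing for an ongoing drug. An aim of over-reporting when in doubt does not cover a case where the recorded date leaves no doubt.

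A fair caution concerns the remedy. Classifying by onset alone could drop an event that began earlier and worsened after the dose. Protocol section 8.1 asks for the most intense severity to be reported, while section 8.1.1 asks for a new record when severity changes, so one cannot rely on a separate record existing.

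**Conclusion.** The rule is wrong as written, within a narrow scope: unresolved partial dates, on records ongoing at or ending after Day 1, whose known month or year precedes vaccination. All of these are recoded to Day 1.

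The practical effect is chiefly long-standing drugs shown as new in one by-participant listing. This assumes that the listing selects on a start date on or after Day 1, since the SAP does not define the term. The misdating can run to years for a chronic drug. A serious event wrongly counted as treatment-emergent is possible but rare, at 0.7 to 1.0 percentage points per event in a group of 150 to 100. The documents do not give the number of partial dates, so no total can be stated. This is a minor correction to make because it is cheap, and it does not threaten any conclusion of the trial.

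**What to change.** Replace the two bullets in SAP section 11.5 with wording to this effect:

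1. If the known month and year (or the year, when only that is known) equal those of Day 1, and the end date does not contradict it, impute Day 1.
2. In all other cases impute the first of the known month, or 1 January of the known year. This includes records that the end-date check blocks from Day 1.
3. Classify records with a known earlier start as prior or not treatment-emergent. The exception is an adverse event that worsens on or after the dose, which remains treatment-emergent under Protocol section 8.1.4.1.

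Ambiguous dates keep their conservative handling, and dates after Day 1 are unchanged. The cost is a few sentences in the SAP and a small change to the date derivation. No new data are needed, and no immunogenicity output has to be rerun.

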### **9.3.3 Safety Analyses**

To describe the overall safety of ancestral strain and updated (if administered) Novavax vaccine(s) administered as a second (or subsequent) booster following licensed mRNA vaccines and a first ancestral strain Novavax vaccine booster, the secondary endpoints of safety data include solicited AEs in the 7 days following study vaccination and MAAEs, AESIs (including myocarditis and/or pericarditis), and SAEs throughout the study. All safety analyses will be descriptive and conducted using the Safety Analysis Set.

All local/systemic solicited (reactogenicity) AEs within the post-vaccination window (Days 1-7) by the verbatim terms, and by severity (mild, moderate, severe) using the maximal severity observed for the specific symptom post-vaccination will be summarized for each study vaccine group.

Unsolicited MAAEs, AESIs (including myocarditis and/or pericarditis), and SAEs throughout the study will be summarized by the study vaccine group and by SOC and PT using MedDRA terms, as well as by severity and relationship to the study vaccine to present the number and percentage with its corresponding exact 95% CIs using Clopper-Pearson method. For multiple occurrences of an AE in the same participant, a participant will be counted only once within an SOC or a PT, using the most severe occurrence and closest reported relationship for the summarization by severity or relationship to the study vaccine, respectively. The duration of MAAEs, AESIs, and SAEs through Day 181 will also be summarized.

A by-participant listing of MAAEs, AESIs, and SAEs throughout the study will also be provided.

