	To describe the overall safety of ancestral strain and updated (if administered) Novavax vaccine(s) administered as a second (or subsequent) booster following licensed mRNA vaccines and a first ancestral strain Novavax vaccine booster.	
• Incidence, duration and severity of solicited adverse reactions in the 7 days following study vaccination.• Incidence, duration, severity, and relationship of medically attended adverse events (MAAEs) and adverse events of special interest (AESIs), (including myocarditis and/or pericarditis) through Day 180 after the vaccine dose.• Incidence and relationship of serious adverse events (SAEs) through Day 180 after the vaccine dose.
Exploratory	To utilize additional assays (current or to be developed) to best characterize the immune response for future vaccine development needs, including testing against emerging variants of SARS-CoV-2.	Additional endpoints to evaluate immune responses may be developed based on the assays used.

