7.3 Analyses of Secondary Endpoint of Safety

As the secondary objective of describing the overall safety of ancestral strain and updated (if administered) Novavax vaccine(s) administered as a second (or subsequent) booster following licensed mRNA vaccines and a first ancestral strain Novavax vaccine booster, safety data include Solicited AEs, unsolicited AEs through Day 29 after the vaccination dose, MAAEs and AESIs (including myocarditis and/or pericarditis) through Day 181 after the vaccine dose and SAEs Day 181 after the vaccine dose. All safety analyses will be descriptive and conducted using the Safety Analysis Set. Missing data will not be imputed.

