7.3.2 Unsolicited Adverse Events

A MAAE is defined as an AE that leads to an unscheduled visit to a healthcare practitioner. All MAAEs will be reported from the time of study vaccination through Day 29. After Day 29, MAAEs attributed to study vaccine will be captured until EOS. AESIs include PIMMCs, myocarditis and/or pericarditis ([Table 11](#) in Appendix 4), and complications specific to COVID-19 ([Table 9](#) in Appendix 2). SAE is an event considered “serious” if, in the view of either the Investigator or Sponsor, it results in any of the outcomes listed in Section 8.1 of the Study 312 Protocol.

Unsolicited MAAEs through Day 29, and MAAEs attributed to study vaccine/AESIs/SAEs throughout the study will be summarized by the study vaccine group and by SOC/PT using the latest version of MedDRA, as well as by severity (Mild, Moderate, Severe) and relationship (not related, related) to the study vaccine to present the number and percentage with its corresponding exact 95% CIs using Clopper-Pearson method. For multiple occurrences of an AE in the same participant, a participant will be counted only once within an SOC or a PT, using the most severe occurrence and closest reported relationship for the summarization by severity or relationship to the study vaccine, respectively.

The duration of MAAEs through Day 29, MAAEs attributed to study vaccine after Day 29 until EoS, AESIs and SAEs throughout the study will be summarized and their corresponding by-participant listings will also be provided.

The following summaries of all unsolicited AEs will be presented by the study vaccine group as the part of safety stated as the secondary endpoints:

- Overall summary of all unsolicited TEAEs (Days 1 – 29)
- Summary of all unsolicited TEAEs by MedDRA SOC/PT and severity (Days 1 – 29)
- Summary of all unsolicited TEAEs by MedDRA SOC/PT and relationship to the study vaccine (Days 1 – 29)
- Summary of MAAEs by MedDRA SOC/PT and severity (Days 1 – 29)
- Summary of MAAEs by MedDRA SOC/PT and relationship to the study vaccine (Days 1 – 29)

- Summary of MAAEs attributed to study vaccine by MedDRA SOC/PT and severity (Days 1 – 29) and (Days 1 – 181)
- Summary of AESIs (including PIMMCs, myocarditis or pericarditis, and complications to COVID-19) by MedDRA SOC/PT and severity (Days 1 – 29) and (Days 1 – 181)

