- Summary of AESIs (including PIMMCs, myocarditis or pericarditis, and complications to COVID-19) by MedDRA SOC/PT and relationship to study vaccine (Days 1 – 29) and (Days 1 – 181)
- Summary of SAE by MedDRA SOC/PT and severity (Days 1 – 29) and (Days 1 – 181)
- Summary of SAE by MedDRA SOC/PT and relationship to study vaccine (Days 1 – 29) and (Days 1 – 181)
- Duration of MAAEs (Days 1 – 29)
- Duration of MAAEs attributed to study vaccine (Days 1 – 29) and (Days 1 – 181)
- Duration of AESIs (Days 1 – 29) and (Days 1 – 181)
- Summary of unsolicited AEs leading to the discontinuation of study (Days 1 – 29) and (Days 1 – 181)
- Summary of SAEs leading to the discontinuation of study (Days 1 – 29) and (Days 1 – 181)
- Listings of all unsolicited AEs including MAAEs, AESIs (including PIMMCs, myocarditis or pericarditis and complications to COVID-19) and SAEs

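### Durations of MAAEs, AESIs and SAEs, and of solicited reactions still open past Day 7, have no rule for events without an end date, so the summaries as planned rest on resolved events and run short

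*SAP*

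**What the plan says.** **Duration as an endpoint.** SAP section 2 (Table 3), like the protocol's synopsis and Table 2, includes duration in two secondary safety endpoints: "Incidence, duration and severity of solicited adverse reactions in the 7 days following study vaccination" and "Incidence, duration, severity, and relationship of medically attended adverse events (MAAEs) and adverse events of special interest (AESIs"). The SAE endpoint does not include it: "Incidence and relationship of serious adverse events (SAEs) through Day 180 after the vaccine dose".

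**Planned summaries.** Protocol 9.3.3 says "The duration of MAAEs, AESIs, and SAEs through Day 181 will also be summarized". SAP 7.3.2 plans duration summaries for MAAEs and adds that "AESIs and SAEs throughout the study will be summarized and their corresponding by-participant listings will also be provided". Its output list has MAAE duration for Days 1–29, vaccine-attributed MAAE duration for Days 1–29 and Days 1–181, and "Duration of AESIs (Days 1 – 29) and (Days 1 – 181"). SAE duration is in the text of 7.3.2 but not in that list.

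**Rules that bear on an open event.** SAP 11.5 says "No imputations will be made to event ending dates". SAP 7.3 says of the safety data "Missing data will not be imputed". Neither document gives a duration formula for unsolicited events, a censoring rule or a time-to-resolution method.

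**Solicited reactions.** SAP 7.3.1 defines three durations: (1) the count of diary days with the reaction, (2) first to last diary day within the 7-day period, and (3) the span including continuation past Day 7, which takes its end from the linked unsolicited AE. The number of participants whose reaction continues beyond Day 7 is also reported.

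**The concern.** Duration needs an end date, and an event in progress at the cut has none. A site query cannot supply one. The documents expect such events: Protocol 8.1.2.4 has outcome categories for events not resolved and still resolving, and Protocol 8.2 lets follow-up of SAEs and AESIs stop once an event is chronic or stable, so some may never acquire an end date.

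The SAP handles other gaps in AE data explicitly. Section 11.5 gives rules for partial onset dates and two conventions each for missing severity and missing relationship. For the end date it only forbids imputation. A programmer following the text computes end minus start where both exist and leaves the rest blank. The blanks are not a random sample: for a given onset day, the events still open at the cut are those that last longest. The resulting mean or median is too short, and nothing in the planned duration tables shows how many events are missing from it.

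**Working it through.** **1. The SAP's own examples.** Method 1, fever on Days 2, 3 and 5: count = 3 days. Method 2, same data: 5 − 2 + 1 = 4 days. Method 3, Days 3, 4 and 6 with a linked AE ending on Day 8: 8 − 3 + 1 = 6 days. All three agree with SAP 7.3.1.

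**2. The same formulas for an open event.** A reaction reported on Days 5, 6 and 7 and still present has duration 3 by method 1 and 7 − 5 + 1 = 3 by method 2: truncated at Day 7, but not missing. Method 3 has no value until the linked AE has an end date. An MAAE, AESI or SAE without an end date has no value for end − start + 1 either.

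**3. Illustrative size.** The documents give no MAAE or AESI durations, so everything here is assumption: durations exponential with true mean m, and available follow-up from onset to cut uniform between a and b days. With L = b − a:

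- Proportion ongoing: p = (m/L)(e^(−a/m) − e^(−b/m))
- Resolved-only mean: (m − q)/(1 − p), where q = (m/L)[(2m + a)e^(−a/m) − (2m + b)e^(−b/m)]

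Example, Day 29 cut with onset uniform over 28 days (a = 0, b = 28) and m = 14: p = 0.5 × (1 − e^(−2)) = 0.432; q = 0.5 × (28 − 56 × 0.1353) = 10.21; resolved-only mean = (14 − 10.21)/0.568 = 6.7 days.

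| Cut and onset | a, b | True mean m (days) | Ongoing | Resolved-only mean (days) |
|---|---|---|---|---|
| Day 29, onset uniform over 28 days | 0, 28 | 7 | 24.5% | 4.9 |
| | | 14 | 43.2% | 6.7 |
| | | 30 | 65.0% | 8.0 |
| Day 181, onset in first 28 days | 152, 180 | 14 | 0.0% | 14.0 |
| | | 30 | 0.4% | 29.3 |
| | | 60 | 6.3% | 48.8 |
| | | 365 | 63.5% | 76.8 |
| Day 181, onset uniform over 180 days | 0, 180 | 60 | 31.7% | 36.6 |
| | | 365 | 78.9% | 55.2 |

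Medians behave the same way. In a simulation with exponential true medians of 5 to 40 days, the resolved-only median at the Day 29 cut is 3.7 to 7.3 days, with 25% to 79% ongoing.

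**4. Which Day 181 row applies.** After Day 29 only vaccine-attributed MAAEs are collected (Protocol 8.1.4.3, SAP 7.3.2), so MAAE onsets should cluster early and the first-28-days rows are the better guide. AESIs and SAEs are collected to end of study and can start late, so the uniform rows are possible for them.

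**5. Start date of a continuing reaction.** Protocol Table 1 footnote 9, Protocol 6.1.3 and SAP Table 7 footnote 9 give the AE the same start date as the reaction; Protocol 8.1.4.4 gives it a start at Day 8. In the method 3 example, the linked AE's own duration is 8 − 3 + 1 = 6 days under one rule and 8 − 8 + 1 = 1 day under the other.

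**The case against.** The strongest reply is that the documents never say ongoing events are dropped. SAP 7.3.2 says only that durations will be summarized, and the sentence in 11.5 stands among rules for partial dates, where it stops end dates being invented. That is correct: exclusion is inferred from silence, and not imputing end dates is sound practice. But the SAP offers no alternative treatment, so exclusion is the default result of following it.

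A reader might infer that all AE durations are affected. They are not. Solicited methods 1 and 2 give every diary-reported reaction a value, the solicited endpoint is confined to 7 days, and the number continuing beyond Day 7 is reported.

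A reader might also infer that the safety conclusion as a whole is made to look better. The documents do not support that. Safety is descriptive, no criterion uses duration, incidence, severity and relationship tables count open events in full, and by-participant listings are planned. The listings would let a reader find open events but would not correct the summary. Nor do the documents say how often the listed immune-mediated conditions remain unresolved at Day 181, so no weight is put on that.

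Finally, with 100–150 participants per group, AESIs may be too few for a Kaplan-Meier estimate. This stands, and is why a simpler display is needed as a fallback.

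**Conclusion.** The gap is real but limited. It covers MAAE and AESI duration (part of a secondary endpoint), SAE duration (a planned summary, not part of the SAE endpoint), and solicited method 3 when the linked AE is open. Followed as written, the plan summarizes resolved events only and understates duration.

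The problem is mainly at the Day 29 analysis: under the stated assumptions a true mean of 7 to 30 days appears as 4.9 to 8.0 days. At Day 181 it is negligible for early-onset events with a mean of 30 days or less (0.4% ongoing at a mean of 30) and matters only for long-lasting or late-onset events. The direction of the bias follows from the rules once open events are left out; its size depends on the assumed exponential durations and onset pattern, for which the documents have no data. This is a cheap improvement to the SAP; it does not touch the immunogenicity endpoints or the other safety tables.

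**What to change.** In SAP 7.3.2, and in 7.3.1 for method 3:

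- Define duration as end date minus start date plus 1.
- Treat an event without an end date as censored at the data cut or last contact, whichever is earlier.
- Report the number of ongoing events beside every duration summary, at both the Day 29 and final analyses.
- Give a Kaplan-Meier median where there are enough events; otherwise show each ongoing event as lasting more than x days.
- Keep the rule in 11.5 against imputing end dates. Censoring does not require imputation.
- Reconcile the start date of a reaction continuing past Day 7 between Protocol Table 1 footnote 9, Protocol 6.1.3 and SAP Table 7 footnote 9 on one side and Protocol 8.1.4.4 on the other.

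The cost is a few lines of SAP text and one extra column in the duration tables, with no new data collection. The downside is that medians may not be estimable when events are few or mostly ongoing; the count of ongoing events still tells the reader what the summary leaves out.
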